6.2.3. Eligibility for Buprenorphine Intervention: Exclusion Criteria

1. Current active addiction to substances other than tobacco, defined as probable moderate-severe substance use disorder for which evidence-based addiction treatment is indicated. This criterion may be identified by any of the following:
 - Patient self-report on eligibility interview
 - Documentation of probable substance use disorder during initial 24 weeks of study
 - Probable substance use disorder based on available clinical information and standardized assessment using the TAPS tool⁵⁹
2. ALT, AST, or total bilirubin $>2X$ the upper limit of normal based on the most recent available laboratory studies obtained within the preceding 12 weeks.
3. History of long QT syndrome, family history of long QT syndrome, or use of Class IA or Class III anti-arrhythmic medications. Class 1A anti-arrhythmic medications used in the outpatient setting include quinidine, procainamide, and disopyramide. Class III anti-arrhythmic medications include amiodarone, sotalol, dofetilide, and dronedarone.
4. Known allergy or prior intolerance to buprenorphine
5. Current use of buprenorphine

6.2.3.1. Childbearing Potential

A person of childbearing potential has experienced menarche and has not undergone successful sterilization or is not postmenopausal. Postmenopausal is defined as amenorrhea for ≥ 12 consecutive months without another cause.

Acceptable forms of contraception include:

- Intrauterine device or hormonal contraceptive implant
- Consistent use of hormonal contraception (depot medroxyprogesterone, combined oral contraceptive; contraceptive patch or ring)
- Consistent use of a barrier method with spermicide (diaphragm, condom, cervical cap)
- Partner who has undergone surgical sterilization
- Abstinence from sexual intercourse

6.2.4. Buprenorphine Formulations

Multiple buprenorphine formulations are FDA-approved for either pain or OUD. Formulations approved for pain (buccal and transdermal buprenorphine) are generally lower strength than those approved for OUD.

Because patients enrolled in this study are expected to be using opioids at a wide range of dosages, more than one buprenorphine formulation will be included as treatment options: sublingual buprenorphine/naloxone and buccal buprenorphine.

6.2.4.1. Sublingual Buprenorphine/Naloxone (Suboxone or Generic Equivalent)

Sublingual buprenorphine/naloxone (Suboxone and generic equivalents) is approved for opioid dependence/OUD. Naloxone is included to deter abuse of the medication by injection, but is inactive when the medication is taken sublingually as directed. Advantages of sublingual buprenorphine/naloxone over buccal (or transdermal buprenorphine) include wide availability with multiple generic products, relatively low cost, ability to efficiently titrate to higher dosages as needed for patients with a high degree of opioid tolerance/dependence, and widespread prescriber experience with this formulation.

6.2.4.2. Buccal Buprenorphine (Belbuca)

Buccal buprenorphine (Belbuca) is approved for moderate to severe chronic pain requiring around-the-clock opioid therapy. Advantages include low starting dosages. Disadvantages include relatively low upper dosages, higher cost, limited insurance coverage, and the time-consuming recommended approach to initiation for patients on high baseline opioid daily doses.

For the trial, buccal buprenorphine will be used for participants on full agonist opioids of <60 MME/day at the time of buprenorphine initiation, those who are anticipated to have low daily buprenorphine dosage requirements, or those who have other reasons for buccal buprenorphine to be preferred. Sublingual buprenorphine/naloxone will be the preferred formulation for participants on ≥60 MME/day at the time of buprenorphine initiation, those who are thought to have higher daily dosage requirements, or those with other reasons for sublingual buprenorphine to be preferred, such as insurance coverage anticipated to restrict access to alternatives after trial participation ends. In determining the initial medication selection and subsequent medication adjustments, individual clinical factors will be considered together with drug cost and factors that would affect availability to the participant after trial participation is completed.

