6.2.7.2. Crossover Titration Method for Initiating Buprenorphine

For the crossover titration method, buprenorphine is started at very low doses several days before the full-agonist opioid is stopped. Buprenorphine is titrated up over several (typically 3-5) days and the full-agonist opioid is discontinued once the buprenorphine is at a therapeutic dose. Case series demonstrate that the crossover titration method is well-tolerated,⁶⁰ and clinical experience indicates that some patients on long-term opioid therapy for pain prefer this approach because they do not have to experience opioid withdrawal

symptoms before initiating buprenorphine. Belbuca will be used as the buprenorphine formulation for the crossover titration method. Once the participant has up-titrated the Belbuca and discontinued the full agonist opioid, either Belbuca or buprenorphine/naloxone will be used as the maintenance buprenorphine formulation based on the considerations described in **Section 6.2.4**.

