6.2.8. Buprenorphine Dosing Regimens

Dosages and dosing regimens for Belbuca and sublingual buprenorphine/naloxone are shown in **Table 6.2**. For participants using the crossover titration approach to transitioning to buprenorphine, Belbuca will be used to initiate the crossover titration. After the transition, Belbuca will be used for all participants who had been using a full agonist opioid at a dose of <30 MME/day. Belbuca will also be used for participants who had been using a full agonist opioid at a dose of 30-35 MME/day, unless the maximal dose of Belbuca (450 mcg twice daily) is insufficient to manage their symptoms. As detailed in the Buprenorphine Manual of Procedures, the dose of buprenorphine will be adjusted (increased or decreased) based on adequacy of pain control, withdrawal symptoms, and tolerability.

For participants using the traditional approach to transitioning to buprenorphine, either Belbuca or buprenorphine/naloxone can be used as the initial buprenorphine formulation depending on the full agonist opioid MME/day, in accordance with the guidelines in the Buprenorphine Manual of Procedures.

Table 6.2. Buprenorphine Dosing

Formulation	Formulation-Specific Exclusions ¹	Dosage Forms	Typical Dosing Regimens
Buprenorphine buccal film (Belbuca)	1. Use of full agonist opioid at dose >160 MME/day	
• 75 mcg buccal film• 150 mcg buccal film	75 mcg – 450 mcg two times per day
Buprenorphine/naloxone sublingual film (Suboxone or generic equivalent)	1. Use of full agonist opioid at dose <30 MME/day 2. Known hypersensitivity to naloxone	
• 2 mg/0.5 mg sublingual film• 8 mg/2 mg sublingual film	2 mg/0.5 mg – 8 mg/2 mg two to three times per day, not to exceed a total dose of 24 mg/6 mg per day

¹These exclusions are in addition to the overall exclusion criteria for the buprenorphine intervention listed in **Section 6.2.3**. Note that these exclusions apply to the anticipated buprenorphine formulation that will be used immediately following the transition from the full agonist opioid. The exclusion does not apply to dose modifications required after a participant has been transitioned to buprenorphine.

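### Do Sections 6.2.4.2 and 6.2.8 give conflicting buprenorphine formulation rules between 35 and 60 MME/day, and does the buccal maximum clash with dosing up to three times daily?

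*Combined protocol and SAP*

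**What the plan says.** Four places bear on the formulation used after crossover titration.

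- Section 6.2.4.2 sets a general default: "buccal buprenorphine will be used for participants on full agonist opioids of <60 MME/day at the time of buprenorphine initiation". Sublingual buprenorphine/naloxone "will be the preferred formulation for participants on ≥60 MME/day at the time of buprenorphine initiation". Both sentences list alternative grounds joined by *or*, such as expected dose requirement or other reasons to prefer a product. The section adds that "individual clinical factors will be considered together with drug cost" and later availability to the participant.
- Section 6.2.7.2 covers the step after up-titration and says that "either Belbuca or buprenorphine/naloxone will be used as the maintenance buprenorphine formulation based on the considerations described in" Section 6.2.4.
- Section 6.2.8 adds rules at the low end: "Belbuca will be used for all participants who had been using a full agonist opioid at a dose of <30 MME/day", and "Belbuca will also be used for participants who had been using a full agonist opioid at a dose of 30-35 MME/day", with one exception if the maximal buccal dose does not control symptoms. It gives no default above 35 MME/day.
- Table 6.2 lists formulation-specific exclusions: for the buccal film, "Use of full agonist opioid at dose >160 MME/day"; for the sublingual film, "Use of full agonist opioid at dose <30 MME/day".

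On dosing frequency, Section 6.2.8 states the buccal maximum as 450 mcg twice daily, and Table 6.2 lists twice-daily buccal dosing as typical. Section 6.2.9 allows two to three doses a day for either product. Only the sublingual product has a stated daily total, 24 mg/6 mg.

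**The concern.** Two sections address the same decision with different numbers, 60 MME/day in one and 30 and 35 in the other. If Section 6.2.8 is read as ending the buccal default at 35, it no longer matches Section 6.2.4.2 for doses above 35 and below 60 MME/day. That band lies inside the eligible range, which starts at 20 MME/day (Section 6.2.2). It is also on the main pathway: Section 6.2.7 makes crossover titration the generally preferred method and requires it for long-acting opioids.

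The buccal ceiling raises a second question. If three daily doses are allowed and the maximum is stated only for two, a reader may ask whether 450 mcg is a limit per dose or part of a daily total. The two products differ in strength, micrograms against milligrams. If the text really gave opposing instructions, sites could treat similar participants differently, and the buprenorphine findings would be harder to interpret.

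**Working it through.** No power, sample size or error-rate figure depends on this point. The check sets the rules side by side and adds simple arithmetic.

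**Formulation by full-agonist dose**

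| MME/day | Section 6.2.4.2 | Section 6.2.8 text | Table 6.2 |
|---|---|---|---|
| 20 to <30 | buccal | buccal for all | sublingual excluded |
| 30 to 35 | buccal | buccal, one exception | both permitted |
| >35 to <60 | buccal, individual factors weighed | silent | both permitted |
| 60 to 160 | sublingual preferred | silent | both permitted |
| >160 | sublingual preferred | silent | buccal excluded |

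1. No row has one section requiring a product that another forbids.
2. In the >35 to <60 row only one default is stated, that of Section 6.2.4.2. Section 6.2.7.2 makes it apply after crossover by pointing to Section 6.2.4.
3. Section 6.2.8 is equally silent in the 60 to 160 row, where nobody would see a conflict. Silence that is harmless there is harmless between 35 and 60. The supposed band appears only if silence is read as an unstated end to the buccal default.
4. The 30-35 rule is not redundant beside a default below 60. Section 6.2.4.2 lets cost, coverage and expected dose requirement change the choice; Section 6.2.8 narrows that latitude at low doses to a single exception. On this reading the two sections stack without collision.

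**Daily totals**

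- Sublingual, from Table 6.2: 3 x 8 mg/2 mg = 24 mg/6 mg, which equals the stated daily limit. Consistent.
- Buccal, as worded in Section 6.2.8: 2 x 450 = 900 mcg/day.
- Buccal, if 450 mcg were a per-dose limit used three times: 3 x 450 = 1,350 mcg/day, and 1,350/900 = 1.5. This figure requires setting aside the twice-daily part of the stated maximum.
- Three doses remain within 900 mcg/day when each is at most 900/3 = 300 mcg, so a third daily dose does not in itself breach the maximum.

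These totals show what each reading implies; none is put forward as the correct dose.

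**How many participants**

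Section 10.3 expects at least 40 eligible participants. At 40 offered, Table 10.6 shows 10, 20 or 30 initiating (25%, 50%, 75%). No Week 24 dose distribution is given, so the number in the band could be 0 to 10, 0 to 20 or 0 to 30. That covers every possible value and is not an estimate.

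**Reach into the analysis**

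The acceptability, tolerability and efficacy analyses in Sections 10.3.1 to 10.3.3 treat buprenorphine as one intervention and are not split by formulation. The primary comparison is at Week 12, before anyone is offered buprenorphine at Week 24.

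**The case for a change.** The best case for acting runs as follows. Two sections govern one choice, and the protocol never says how they fit together. Section 6.2.8 cites the Buprenorphine Manual of Procedures for dose adjustment and for the traditional method, but not for the formulation after crossover, so the protocol text has to carry that rule. Each enrolling site has at least two prescribers (Section 6.2.6), and there are 14 recruitment sites (Section 10.2.1). Section 11.8 counts dosing errors among its examples of major deviations, so an unclear ceiling could leave compliance open to argument. The amendment history shows that V1.3 moved the sublingual exclusion in Table 6.2 from below 60 to below 30 MME/day and lists no matching edit to Section 6.2.4.2, which suggests a leftover number.

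Part of this stands. The relation between Sections 6.2.4.2 and 6.2.8 is left to inference, and Section 6.2.9 does not say how the buccal maximum applies to three doses. The references to Section 6.3.x for buprenorphine in Sections 5, 7.4.4, 7.5.1 and 7.5.5 are out of date, since 6.3 is now Usual Care.

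The rest does not carry. A default and an exclusion are different kinds of rule, so changing one did not oblige a change to the other, and the log describes the V1.3 text in Section 6.2.8 as further guidance. Treatment in this phase is individualised by design (Sections 6.2.1 and 6.2.7), so variation between prescribers is intended. Doses are adjusted to response, and Section 6.2.7.4 schedules four follow-up visits in the first three weeks.

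**Conclusion.** The concern does not call for a change to the plan. Above 35 and below 60 MME/day there is one stated default with room for judgement, and either product can comply. What remains is missing detail and clerical tidying: how Sections 6.2.4.2, 6.2.7.2 and 6.2.8 fit together, how the buccal maximum in Section 6.2.8 relates to the frequency in Section 6.2.9, and the stale 6.3.x references. These passages must be reconciled, and that is for the clinical investigators; nothing here says which threshold, product or dose is right.

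Followed as written, the plan produces no wrong result. No stated number, analysis or conclusion changes, and the Week 12 comparison is untouched. This rests on two things: that silence in Section 6.2.8 is read as silence and not as an implied rule, and that the Phase 2 analyses remain pooled over formulation as Section 10.3 describes. The Buprenorphine Manual of Procedures was not available. It may already settle the working rule, but the conclusion does not depend on it.

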6.2.5. Buprenorphine Regulatory Issues

With few exceptions, federal regulations prohibit clinicians from prescribing opioids for the purpose of treating OUD. One exception is for sublingual buprenorphine, which is FDA-approved for the treatment of OUD. Physicians and advanced practice providers may complete specific training and apply for a waiver through the DEA that authorizes them to prescribe sublingual buprenorphine for OUD. Importantly for this trial, the DEA clarified in 2004 that clinicians may prescribe sublingual buprenorphine “off-label” without a waiver. Use of sublingual buprenorphine in this protocol is for physical dependence due to prescribed long-term opioid therapy for pain, not for OUD; therefore, study prescribers are not required to have a waiver regardless of which buprenorphine formulation is prescribed.

6.2.6. Buprenorphine Prescribing and Dispensing

Each enrolling site will designate at least two study physicians as buprenorphine prescribers. Study physicians will prescribe buprenorphine for participants who are eligible for and elect to switch to buprenorphine after obtaining informed consent specifically for buprenorphine. Buprenorphine prescriptions written by authorized study prescribers will be transmitted to the central investigational pharmacy and the medication will be mailed by the investigational pharmacy to the participant in specified intervals throughout the study period.

Participants will use study-provided mailers to return medication containers to the investigational pharmacy for dose counting and return of unused drug. For participants enrolled from the Veterans Affairs (VA) Healthcare System sites, all of the activities described above will be completed by the local VA pharmacy for each site.

6.2.7. Buprenorphine Initiation

Decisions about how to initiate buprenorphine will be individualized based on the participant's needs and preferences as well as the prescriber's experience and local resources. Participants may initiate buprenorphine at home or in the study physician's office. There are two methods for switching from full-agonist opioids to either buccal or sublingual buprenorphine: a traditional method and a newer crossover titration method.⁶⁰ The approach used for individual participants will be at the discretion of the study physician prescribing the buprenorphine; however, in general, the crossover titration method is preferred, and required for participants using long-acting opioid medications.

6.2.7.1. Traditional Method for Initiating Buprenorphine

For the traditional method, full-agonist opioids are stopped entirely prior to starting buprenorphine. The interval between last dose of the full-agonist opioid and the first dose of buprenorphine depends on the duration of action of the full-agonist opioid. In most cases, 12-18 hours is appropriate for short-acting opioids. For long-acting opioids, a longer interval is typically needed (approximately 18-24 hours for morphine SA). Patients using the traditional method for switching to buprenorphine will be advised that they will experience opioid withdrawal symptoms during the interval after stopping full-agonist opioids and before starting buprenorphine. For participants using long-acting opioids (e.g., oxycodone controlled-release, morphine controlled-release tablet or capsule, oxycodone controlled-release, oxymorphone extended-release hydromorphone extended-release, fentanyl transdermal), the crossover method will be used rather than the traditional method in order to avoid the need for prolonged periods without use of either the full agonist opioid or buprenorphine.

6.2.7.2. Crossover Titration Method for Initiating Buprenorphine

For the crossover titration method, buprenorphine is started at very low doses several days before the full-agonist opioid is stopped. Buprenorphine is titrated up over several (typically 3-5) days and the full-agonist opioid is discontinued once the buprenorphine is at a therapeutic dose. Case series demonstrate that the crossover titration method is well-tolerated,⁶⁰ and clinical experience indicates that some patients on long-term opioid therapy for pain prefer this approach because they do not have to experience opioid withdrawal

symptoms before initiating buprenorphine. Belbuca will be used as the buprenorphine formulation for the crossover titration method. Once the participant has up-titrated the Belbuca and discontinued the full agonist opioid, either Belbuca or buprenorphine/naloxone will be used as the maintenance buprenorphine formulation based on the considerations described in **Section 6.2.4**.

6.2.7.3. Information for Participants About Initiation of Buprenorphine

Precipitated opioid withdrawal is the main potential adverse effect of switching to buprenorphine; however, this can be avoided by adhering to the initiation protocol. When using the traditional method for switching to buprenorphine, the most critical point patients need to understand is that the full agonist opioids must be sufficiently cleared from the body before buprenorphine initiation. This means that participants must wait for the onset of at least moderate withdrawal symptoms. When using the crossover titration method, the critical point is to start at a very low dose and increase according to instructions over several days. All patients will be provided detailed written and verbal information about opioid withdrawal symptoms and about precipitated withdrawal. Understanding will be confirmed by teach-back.

6.2.7.4. Initial Visit with Buprenorphine Prescriber

Participants who meet eligibility criteria for the Phase 2 buprenorphine intervention will be scheduled as soon as convenient for a visit (in-person or by video) with a study physician who will prescribe the buprenorphine. Substance use testing using saliva will be performed prior to the initial visit with the buprenorphine prescriber.

The initial buprenorphine visit will be an in-person or video-based visit with the study buprenorphine prescriber, as described above. First visit tasks include the following:

- Obtain history of prescription and non-prescription opioid use and substance (alcohol, drug) use and assess for substance use disorder; assess buprenorphine risk factors (including risk for pregnancy if applicable)
- Provide standardized buprenorphine educational materials and resources
- Discuss benefits and risks of buprenorphine use and provide instructions to reduce risks such as dental problems
- Recommend buprenorphine and use shared decision-making to establish a plan for buprenorphine initiation and follow up; provide information about who should be contacted if problems or concerns occur between visits
- Complete informed consent process for initiating buprenorphine

Buprenorphine administration will not occur at the initial buprenorphine visit. After the initial visit has been completed and written informed consent is obtained, the study physician will prescribe buprenorphine, which will be mailed to the patient's home. Patients will self-administer buprenorphine, typically at home, as described above.

Following buprenorphine initiation, structured follow-up will occur at multiple time points within the first 3 weeks after buprenorphine initiation. These follow-up visits will occur at 2-3 days, 1 week, 2 weeks, and 3 weeks after initiation, but the timing can be modified based on the judgement of the buprenorphine

prescriber. These visits will be conducted by the buprenorphine-prescribing study physician. Most visits will be conducted by telephone, but they may be conducted in-person or by video if preferred. After these four structured visits, follow up will occur at a frequency determined by the buprenorphine prescriber but will include follow-up at Weeks 32 and 36 during which plans for post-trial pain management will be discussed (see Section 6.2.9). Follow-up visit tasks include the following:

- Assess medication response and adverse effects, including withdrawal symptoms as appropriate
- Administer standard satisfaction questions
- Provide additional education or counseling as needed
- Perform substance use testing using saliva at the discretion of the buprenorphine prescriber in a manner consistent with standard clinical care
- Plan for post-trial pain management (Week 32 and Week 36 visits)

